7.2.3 Consent

Participant Consent – Potential participants will be afforded sufficient time to consider whether or not to participate in this research study. If the ostomate agrees, informed consent will be obtained. If patients wish to have more time prior to signing the consent, they may mail back the consent. For potential participants contacted over the phone, the same information will be relayed, and they will be asked to mail the consent prior to randomization. Participants will complete the baseline assessment following informed consent.

Caregiver Consent – Participants will designate their caregivers upon registration. It can be anyone they feel they want in that role for this study. As with participants, caregivers will need to have signed a consent prior to participation. Only some basic information will be obtained for caregivers, including age, gender, relationship, and current work status. This will be maintained in a study sheet for every patient. Appendix 11

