5.0 ELIGIBILITY CRITERIA

5.1 Eligibility criteria

1. Cancer survivors over 21 years of age having undergone a procedure that needed an intestinal stoma (fecal or urinary). Survivors with temporary ostomies will be included.
2. All participants must have a full understanding of the protocol and be able to sign an informed consent form.
3. Having an identified caregiver is **not** a requirement for eligibility.
4. All participants will attend their first training session at least six weeks after their operation.
5. There is no maximum time since surgery.

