7.2.1.4 Yale-New Haven

The Yale Research Assistant will work in collaboration with the site-PI ([name]) and site-Col ([name]) to identify potential participants for the study. Potential participants must meet eligibility criteria outlined in the study protocol. Potential areas of recruitment include the outpatient setting (ostomy or post-surgical clinics) and inpatient surgical units of the Yale New-Haven Hospital system and Smilow Cancer Center. The appropriate medical and nursing staff involved in the care of these patients will be contacted about the study a priori and a method of communication and referral will be established between the clinical and research staff. We will be in close touch with these referral sources on a daily basis to identify potential patients.

The clinical staff will approach the patient and ask for his or her permission for the RA to contact them. Having this permission, the RA will approach the patient to describe and explain the study purpose, study groups (OSMT training group versus Usual Care Group), randomization procedures, study procedures, and human subjects' protection concerns (right to withdraw, confidentiality, risks and benefits, etc.).

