The COH QOL-CRC assesses ostomy burden and care abilities, including time taken to perform daily ostomy care, comfort with ostomy care, comfort with diet, adjustment of diet for ostomy, appetite, clothing and other problems with ostomy placement. We will also measure clinically related outcomes, including medical attention for problems with bowel, bladder, or ostomy. Changes in these responses will be compared between treatment groups with linear mixed models, chi-square tests or t-tests, as appropriate.

Descriptive statistics will be presented on attendance at training sessions. We will describe and contrast quantity and type of ostomy-care help (professional and lay) sought outside of the training sessions, including calls for support from study Peer Ostomates. Self-reported Peer Ostomate call frequency and duration will be corroborated with a call log maintained by the Peer Ostomate. We will evaluate hypothesized association between OSMT attendance level and outcomes using linear mixed models that have a weighted attendance score as an independent variable. Alternative attendance scores will be tested that give weight to ostomy-care help outside of training sessions.

12.3 Aim 2: Determine the differences in ostomy-related **medical care utilization** and family **financial burden** imposed on survivors between OSMT and UC groups.

Hypothesis 2.1: OSMT telehealth subjects will use fewer **ostomy-specific** family resources in the 6 months after OSMT compared to UC subjects.

Hypothesis 2.2: OSMT telehealth subjects will use fewer **ostomy-specific** health care services in the 6 months after OSMT compared to UC subjects.

Question 2.1: What is the difference in the overall levels of **ostomy-related** family financial burden between OSMT and UC groups?

Question 2.2: What are types and levels of effort of OSMT intervention personnel and specific equipment, supplies, and informatics support required to implement and operate a successful OSMT program; what are participants' levels of use of ostomy-specific health care

services and supplies; and what are the time and in-home requirements for participating in OSMT for survivors and their family caregivers. This information is required for replicating our OSMT intervention in the event that we find it improves the primary and secondary outcomes of OSMT participants.

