15.7 Appendix 7a Burden of Ostomy Care Survey (full survey, baseline and followup)

BURDEN OF OSTOMY CARE

This study aims to collect data on the burden associated with families' use of ostomy care and supplies, including ostomy-related medications, ostomy-related health care visits, travel costs to obtain ostomy-related care and supplies, and time spent on ostomy management tasks. We ask that you please answer these questions while thinking specifically about the burden of ostomy-related care. This is not a test; please give us your best estimates based on your personal experience.

1. What kind of Ostomy do you have? Colostomy Ileostomy Urostomy Other

2. In-person Visits with Wound and Ostomy Care Nurse in the past 4 weeks:

- a. Did you visit a Nurse in person in the past 4 weeks (at a medical office, hospital, and/or in your home)? No (If NO, skip to Question 3. below.) Yes
- b. **If YES:** How many times did you visit the Nurse in the past 4 weeks? 1 2 3-4 5-8 More than 8

Please answer questions 2c through 2g thinking specifically about your most recent visit to the Nurse.

- c. How much do you typically pay out-of-pocket for each Nurse visit (copayments, deductibles, or other costs for the visit that weren't covered by your insurance)?
 Nothing \$1-\$10 \$11-\$25 \$26-\$50 \$51-\$75 \$76-\$100 \$101+
- d. Did you have to travel to see the Nurse for your most recent visit? No (If NO, skip to Question 3. below.) Yes
- e. How much do you typically pay out-of-pocket to get to and from each Nurse visit (such as the cost for taxi, bus, or parking)? \$1-\$5 \$6-10 \$11-15 \$16-\$25 \$26-\$50 \$51-\$100 \$101+
- f. Approximately how far did you have to travel to the Nurse Visit location? 1-4 miles 5-8 mi. More than 8 mi.
- g. Approximately how much time did it take you to get from your home to the Nurse Visit location? 1-10 mins 11-30 mins More than 30 mins

3. Telephone and/or email consultations with a Wound and Ostomy Care Nurse in the past 4 weeks:

- a. Did you have any telephone and/or web consultations with the Nurse in the past 4 weeks? No (If NO, skip to Question 4 below.) Yes
- b. **If YES:** How many telephone and/or web consultations have you had with a Wound and Ostomy Care Nurse over the past 4 weeks? 1 2 3-4 5-8 More than 8

Please answer Question 3c thinking specifically about your most recent telephone or web consultation with the Nurse.

- c. How much did you have to pay out-of-pocket for this Nurse consultation?

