Please answer questions 13c through 13f thinking specifically about your most recent Urgent Care visit for stoma and/or bowel function problems.

- c. How much did you pay out-of-pocket for your most recent Urgent Care visit (copayments, deductibles, or other costs for the visit that weren't covered by your insurance)?
 \$0 \$1-\$5 \$6-10 \$11-15 \$16-\$25 \$26-\$50 \$51-\$100 \$101+
 d. How much did you pay out-of-pocket to get to and from the Urgent Care visit (such as the cost for taxi, bus, or parking)? \$0 \$1-\$5 \$6-10 \$11-15 \$16-\$25 \$26-\$50 \$51-\$100 \$101+
 e. Approximately how far did you have to travel to the Urgent Care visit location? 1-4 miles 5-8 mi. More than 8 mi.
 f. Approximately how much time did it take you to get from your home to the Urgent Care visit location? 1-4 minutes 5-8 min. More than 8 min.

14. What type of ostomy bag system are you using? One piece Two piece

15. How many of each of the following have you used over the past 4 weeks?

- a. Wafers: 10 or less 11-20 21-30 31-50 More than 50
 b. Bags: 10 or less 11-20 21-30 31-50 More than 50

16. Medications to manage your bowel function in the past 4 weeks

- a. Have you used any medications to manage your bowel function in the past 4 weeks? (e.g., Imodium®, Metamucil®, Miralax®, Loperamide) No (IF NO, skip to Question 16. below.) Yes
- b. **IF YES:** how many different medications have you used to manage your bowel function in the past 4 weeks? ____
- c. Please list up to three medications you used most frequently to manage your bowel function and the number of days you took these medications in a typical week:
 - i. Medication _____ Number of days used (0 to 7) _____
 - ii. Medication _____ Number of days used (0 to 7) _____
 - iii. Medication _____ Number of days used (0 to 7) _____

17. Do you use the Eakin seal (moldable donut or ring)? No Yes

18. Medications to manage – treat or prevent – skin problems around your stoma in the past 4 weeks

- a. Have you used any prescription medications to manage skin problems around your stoma in the past 4 weeks? (e.g., Nystatin powder). No (IF NO, skip to Question 18. below.) Yes
- b. **IF YES:** how many different medications have you used to manage skin problems around your stoma in the past 4 weeks? None 1-2 3-4 5 or more
- c. Please list up to three medications you used most frequently to manage skin problems around your stoma and the number of days you took these medications in a typical week:

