 - i. Medication _____ Number of days used (0 to 7) _____
 - ii. Medication _____ Number of days used (0 to 7) _____
 - iii. Medication _____ Number of days used (0 to 7) _____

19. How much have you spent on purchases of ostomy appliances (including wafers and bags in total over the past 4 weeks)? \$0 \$1-\$25 \$26-50 \$51-100 \$100-\$150 \$150-\$200 \$200-\$250 over \$250

20. About how many times a day do you empty your drainable ostomy bag (or discard your closed/disposable bag)?

- None 1-4 5-8 More than 8

21. Over the past 4 weeks, what was the highest number of bag emptyings in a 24-hour period?

- None 1-4 5-8 More than 8

22. Over the past 4 weeks, what was the lowest number of bag emptyings in a 24-hour period?

- None 1-4 5-8 More than 8

23. How often do you typically discard a used bag and use a new bag?

- At every emptying Once a day Once every 2-3 days Less often

24. How much time does it usually take you to empty/dispose your bag?

- 1-5 minutes 5-10 minutes 10-15 minutes More than 15 minutes

25. How often do you typically change your wafer on a typical week? 1 2 3 4-7 More than 7

26. How much time does it usually take you to change your wafer and bag?

- 1-15 minutes 16-30 minutes 30-45 minutes 45-60 minutes More than 60 minutes

27. Do you usually receive help caring for your stoma and changing your ostomy appliance?

- a. No (skip to Question 27 below)
- b. Yes IF Yes, please check who your helper(s) is(are):
 Spouse/Significant Other Other family member Friend Home care nurse Other Paid Caregiver Other (please specify) _____

28. Has your bag leaked at any time over the past 4 weeks?

- a. No (skip to Question 28 below)
- b. Yes **IF YES**, how many times? 1-4 5-8 More than 8
- c. How many of these times involved a full spillage of your bag contents? 1-4 5-8
More than 8
- d. How much time does it require to clean up after a bag leak or spill? 1-30 minutes 31-60 mins.
More than 60 mins

29. Do you have waterproof covers on your mattress and primary chair(s)?

- a. No → Skip to Question 29 below.
- b. Yes **IF YES**, how much did you spend to purchase them?
\$0 \$1-\$10 \$11-\$25 \$26-\$50 \$51-\$75 \$76-\$100 \$101-\$150 \$151+

30. Do you have to make alterations to your clothing to accommodate your ostomy appliance?

- a. No **IF NO**, skip to Question 30 below.
- b. Yes **IF YES**, do you make these modifications yourself?
 - i. No
 - ii. Yes → **IF YES**, How much do you spend for these modifications?

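### The baseline burden survey has no minimum time since surgery, so for early enrollees its 4-week counts are not comparable with the 6-month counts

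*Protocol*

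**What the plan says.** Baseline timing is tied to consent alone: "Participants will complete the baseline assessment following informed consent" (Protocol 7.2.3). Section 9.5 refers the reader to 8.1 for baseline, and 8.1 gives no window. Section 7.1 sets a latest registration time but no earliest.

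The one lower limit on time since surgery is in 5.1: "All participants will attend their first training session at least six weeks after their operation". It concerns the session, not consent, randomization or the survey, and usual-care participants have no session. The same list adds "There is no maximum time since surgery". Section 8.1 lets enrollment precede the group's start by up to 2 months.

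At Yale-New Haven (7.2.1.4), "Potential areas of recruitment include the outpatient setting (ostomy or post-surgical clinics) and inpatient surgical units".

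The full Appendix 7a is given at baseline (8.2.1) and again at 6 months (8.2.3). Its items use a fixed look-back:

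- item 2a: "Did you visit a Nurse in person in the past 4 weeks (at a medical office, hospital, and/or in your home";
- item 15, wafers and bags: "How many of each of the following have you used over the past 4 weeks";
- item 28: "Has your bag leaked at any time over the past 4 weeks".

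Physician, emergency and urgent-care contacts and appliance spending use the same 4 weeks. The form has no instruction for a stoma younger than that.

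After naming COH-QOL-CRC items and medical attention for bowel, bladder or ostomy problems, 12.2 and the SAP state: "Changes in these responses will be compared between treatment groups with linear mixed models, chi-square tests or t-tests, as appropriate".

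**The concern.** A person consented and surveyed on the ward reports a 4-week count when the ostomy may be only days old. Supply use, appliance spending and leaks then come out low, because much of the window precedes the operation. Nurse visits can come out high. Item 2a accepts hospital contacts, and the account of usual care in Section 3.0 describes the ostomy nurse teaching patients before discharge.

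At 6 months the same items cover 28 days with an ostomy and, for these participants, no index admission. The two values have different denominators. A rise in supplies or leaks, or a fall in nurse visits, would partly reflect when the survey was taken. The baseline would also predict the follow-up value less well.

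**Working it through.** The plan states no figure on this point, so there is none to reproduce.

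**1. Do the rules allow an early baseline?** Enrollment on day 5 with a first session at the earliest permitted day, 42, gives a gap of 42 − 5 = 37 days. The limit is 2 months (about 59 to 62 days). No rule is broken.

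**2. How much of the window is affected?** Let d be the days from operation to survey and L the length of the index stay. The documents do not give L, so 4 to 14 days is assumed.

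- Pre-ostomy share = max(0, 28 − d)/28.
- Pre-ostomy or admission share = [max(0, 28 − d) + max(0, min(d, L) − max(0, d − 28))]/28.

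| Survey day | Pre-ostomy | Pre-ostomy or admission, L = 7 |
|---|---|---|
| 5 | 82% | 100% |
| 7 | 75% | 100% |
| 14 | 50% | 75% |
| 21 | 25% | 50% |
| 28 | 0% | 25% |
| 42 | 0% | 0% |

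At day 28 the admission still takes up 14%, 25%, 36% or 50% of the window for stays of 4, 7, 10 or 14 days.

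**3. What does it do to pooled exact counts?** All of the following are assumptions:

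- weekly rates follow a gamma distribution with mean 1 and between-person CV 0.8;
- counts are Poisson, with no true change and a constant rate from the operation on;
- a share p is surveyed early, uniformly over days 5 to 28, and the admission is ignored.

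With observed fraction f, an early respondent has mean f = (5/28 + 1)/2 = 0.589 and mean f² = 0.403. Hence E[f] = 1 − 0.411p and E[f²] = 1 − 0.597p.

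- Follow-up variance = 4 + 16 × 0.64 = 14.24.
- Covariance = 10.24 × E[f].
- Baseline variance = 4E[f] + 16 × 1.64 × E[f²] − 16E[f]².
- With r the correlation, residual variance = 14.24 × (1 − r²).

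| p | Baseline mean / true mean | Correlation | Rise in residual variance |
|---|---|---|---|
| 0 | 1.00 | 0.72 | none |
| 10% | 0.96 | 0.70 | 5% |
| 20% | 0.92 | 0.68 | 10% |
| 30% | 0.88 | 0.67 | 15% |
| 40% | 0.84 | 0.65 | 19% |

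A simulation of 400,000 records under the same assumptions gave 6, 11, 16 and 20%. The shortfall in the baseline mean (4 to 16%) reappears as a false increase by 6 months.

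**4. What about the answers as recorded?** Leaks are banded: none, 1–4, 5–8, more than 8. Scoring these bands 0 to 3 in the same simulated model gives rises in residual variance of about 3, 6, 9 and 12%.

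**5. How much does an exposure-adjusted baseline recover?** If the regression slope may depend on f, residual variance at f is 14.24 − 10.24²f/(4 + 10.24f). This is 6.88 at f = 1 and averages 8.35 over the early range, a ratio of 1.214. The rise is then 0.214p, or about 2, 4, 6 and 9%, roughly half the loss in step 3.

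**The case against.** **The early share may be small.** Inpatient units are a potential recruitment area at one site of three. The other sites use clinic lists, ambulatory clinics and tumor boards. There is no upper limit on time since surgery. Surveys go out by web or mail, and non-response is chased only after 2 weeks. This stands: no figure in the documents supports any particular share.

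**Banding blunts the effect.** One leak a week is 4 in 28 days or 1 in 7 days, and both answers fall in 1–4. With pouches worn up to 5 days (Appendix 1), 28 days needs about 6 changes and 7 days about 1 or 2, and both fall in the lowest band of item 15. A reader might carry the 75% at day 7 over to the recorded answers. For banded items that does not follow.

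**Time since surgery is already a candidate covariate in 12.2.** This helps in part. A candidate may be dropped in model selection, and a main effect does not rescale a baseline count.

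Three stronger readings are tempting but unsupported:

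- *The treatment comparison is biased.* Randomization balances time since surgery between arms. The plan does not say that baseline precedes randomization, so one could imagine timing drifting apart by arm, but nothing in the documents shows that it would.
- *Hypotheses 2.1 and 2.2 lose precision as planned.* They compare arms in the 6 months after OSMT, and 12.3 to 12.7 state no change-from-baseline or baseline-adjusted model. The loss arises only if one is used. The sentence on changes in 12.2 covers medical attention but does not name supplies, spending or leaks.
- *A day-28 floor on the survey would cure the problem.* It removes pre-ostomy time but leaves admission days in the window.

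**Conclusion.** The point holds as a limited defect of measurement. Following the plan as written, anyone surveyed less than 28 days after surgery gives 4-week answers that partly cover time without an ostomy, and item 2a can add inpatient teaching visits. Those baseline values should not be set against the 6-month values as they stand.

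The damage is to within-arm change and to the precision of the medical-attention change comparisons in 12.2 and any baseline-adjusted Aim 2 analysis. The arm contrast is not biased. PAM has no 4-week recall, so the primary analysis and its power are unaffected.

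The variance increases, roughly 5 to 20% for exact counts and 3 to 12% for banded leaks, rest on an assumed early share of 10 to 40% and on the rate model above. With a smaller share the effect is correspondingly smaller. The repair is worth making because it is cheap.

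**What to change.** 1. **Form.** In the baseline Appendix 7a, instruct respondents whose discharge after the ostomy operation was less than 4 weeks ago to count only the time since discharge. In item 2a, tell them not to count visits during that hospital stay.
2. **Data and analysis.** Record days since operation and since discharge at the baseline survey, in both arms. Where the window is shorter than 28 days, analyze baseline counts with exposure min(28, days with an ostomy after discharge). For banded items, include an early-baseline indicator and its interaction with the baseline value. Someone surveyed before discharge has zero exposure, so treat the baseline for these items as missing.
3. **Timing, optional.** Where scheduling allows, have the baseline surveys completed before randomization and at least 4 weeks after discharge, with the same rule in both arms. Consent may still be taken earlier.

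Parts 1 and 2 cost a few lines of form text, two recorded intervals and some analysis work, with no extra participants or visits. Part 3 has a real price. Some inpatient recruits would wait between consent and randomization. With a 7-day stay, 4 weeks after discharge is day 35, which leaves only 7 days before a week-6 session for group assignment, mailing and the connection test. It should therefore remain optional.

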7.2.4 Study ID

The study ID will be comprised of 4 digits, in which the first digit denotes the medical center site, and the remaining digits number the consented subjects within the site. For the first digit, 1 =

University of Pennsylvania, 2 = Yale, and 3 = City of Hope. Thus, for example, the first subject consented at City of Hope would have study ID 3001.

7.2.5 Subject Reimbursement

Intervention and Usual Care subjects will receive Greenphire ClinCards in the amount of \$50 at completion of the initial survey, \$50 at completion of surveys at the end of the intervention sessions, and \$50 at completion of the follow-up surveys six months after the end of the sessions, for a total of \$150. Intervention subject caregivers will receive Greenphire ClinCards in the amount of \$25 for each of the two sessions they attend, for a total of up to \$50.

8.0 MAILED PACKETS

Mailed packets will include paper materials, described below. All packets will be mailed from and returned to the subjects' respective medical center to ensure that PHI remains at the respective medical center. To mitigate the risk of mixing surveys from multiple participants, each page of paper surveys MUST have the Study ID pre-entered in its field. No PHI will appear on the survey (other than a separate cover letter). After returned paper surveys are processed at the medical center, they will be shipped to the UA Data Core. For RedCap® web-based survey administration (described below), the subject survey ID (separate from the subject ID and specific to each survey time) will be provided by the UA Data Core to the medical centers. Medical Center coordinators will provide their respective subjects survey ID and survey web link at the appropriate time, but the survey responses will transmit directly to the RedCap® server at the University of Arizona.

8.1 Session Information/Preparation

Site coordinators at the three accrual sites will communicate to each other the number of subjects being assigned to a group as they are randomized to the Intervention arm. When the group enrollment gets to six, they will close enrollment to that group and begin enrolling in the next group. Coordinators will slow enrollment if needed so that subjects are not enrolled in a group starting more than 2 months from the enrollment date. If needed, the team will discuss adding additional groups to the schedule on different dates so that subjects will be able to start within the 2-month window from enrollment date.

For intervention session schedules, the protocol will include two different schedules for intervention session administration. This design is to provide flexibility for participants and also to maximize study accrual and participation. The schedules include:

Schedule #1: Two sessions administered on the same day, with a break in between. There will be a 4-week interval between the first set of 2 sessions and second set of 2 sessions. The caregiver session will be held two weeks after the first set of sessions.

Schedule #2: One session administered per day, once a week over a five-week period. There will be a one-week interval between session 2 and session 3 during which the caregiver session will be held.

The two schedules vary throughout the study period based on participants' convenience and preference.

If a subject misses a session, they can make up just the missed session with the next 1 or 2 scheduled groups rather than start over with a new group. If they miss both Session 1 and Session 2, they can be re-assigned to the next group as long as the next group size doesn't

exceed 6, or at the ostomy nurses' ([name] and [name]) discretion if the group size would exceed 6.

If a subject misses Session 3 or Session 4 or both, they can make up the missed session(s) with the next 1 or 2 scheduled groups. If they miss both chances to make up the sessions, they will be asked to do the surveys and will be analyzed as a separate group using an intent-to-treat contrast.

To account for making up sessions or delays in completing interim surveys, for both intervention and usual care groups, the 6-month followup surveys will be requested from subjects 6 months after the date the interim surveys are completed.

Caregivers who miss the Caregiver session in the subject's assigned group will not be required to make up the session.

At the start of Session 1, the ostomy nurses will review Appendix 9, Group Rules, and remind participants that they can contact their local site Peer Ostomates or ostomy nurses for help.

In any session, if a participant becomes disruptive, it will be noted and if necessary, they will be asked to leave the session. The team will discuss the nature of the disruption and how to handle the participant for future sessions.

